6.1 Outcome

The primary analysis will compare the treatment groups [EndoClean and manual irrigation with sodium hypochlorite (NaOCl)] on their mean difference in post-operative pain sensitivity throughout a week period (6h, 24h, 48h, 72h and 1w). Declared pain scores over time for the patients will be the dependent variable. Study subjects will be considered as random effects, treatment group and visit number as fixed effects. Other variables like Age and Toot-ID can be included as a covariate according to their relations with response variable. The estimated difference in mean change from EndoClean and Control groups and the corresponding 95 % confidence interval (CI) will be presented.

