3.3.1.1. Sample Size Calculation

In order to determine the number of samples, power analysis was performed using the G*Power (v3.1.9.2) program. The power of the study is expressed as $1-\beta$ (β = probability of type II error). Based on the postoperative 6th-hour pain measurements in the article by D. Liapis et al.*, the mean for

Group I was 13.9 SD:16.2; When the mean for Group II was taken as 4.9 SD: 7.3, the effect size (d) was found to be 0.716 in the calculation made to obtain 90% power at the $\alpha=0.05$ level. Accordingly, it was calculated that there should be at least 42 people in each group and 84 people in total. Considering that there may be losses during the study process (20%), it was decided to take at least 50 people in each group.

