2.1. Sample Size Calculation

In order to determine the number of samples, power analysis was performed using the G*Power (v3.1.9.2) program. The power of the study is expressed as $1-\beta$ (β = probability of type II error). Based on the postoperative 6th-hour pain measurements in the article by D. Liapis et al.*, the mean for Group I was 13.9 SD:16.2; When the mean for Group II was taken as 4.9 SD: 7.3, the effect size (d) was found to be 0.716 in the calculation made to obtain 90% power at the $\alpha=0.05$ level. Accordingly, it was calculated that there should be at least 42 people in each group and 84 people in total. Considering that there may be losses during the study process (20%), it was decided to take at least 50 people in each group.

10 patients will be involved in a pilot study. There will be 5 patients in each group: manual final irrigation and EndoClean device. Pilot study will be conducted for two reasons. The first reason is to ensure the safety of the device for clinical use. The second reason is to conduct an accurate power analysis and therefore, a sample group for the full clinical study. A full clinical investigation will be performed once the pilot study is done, and which will be powered according to the outcome of the pilot study.

3. Objectives

The primary objective of this randomized controlled trial is to compare the postoperative pain intensity levels in patients with asymptomatic teeth diagnosed for non-surgical orthograde root canal treatment that are disinfected during the root canal treatment procedure by manual irrigation with

sodium hypochlorite (NaOCl) solution or EndoClean. The secondary objective is to evaluate, if EndoClean could be used safely during root canal treatment as an alternative approach to manual irrigation.

4. Outcomes

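### The stated 90% power is for 6-hour pain alone and is not the power of the five-visit treatment effect that SAP 6.1 makes primary

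*SAP*

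**What the plan says.** **Sizing.** SAP 2.1 rests on one time point: "Based on the postoperative 6th-hour pain measurements". Protocol 3.3.1.1 has the same text. Both assume means of 13.9 (SD 16.2) and 4.9 (SD 7.3). The protocol then says that "the effect size (d) was found to be 0.716 in the calculation made to obtain 90% power", and that "it was calculated that there should be at least 42 people in each group and 84 people in total". For attrition: "Considering that there may be losses during the study process (20%), it was decided to take at least 50 people in each group".

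**Primary analysis.** SAP 6.1 compares the groups "on their mean difference in post-operative pain sensitivity throughout a week period (6h, 24h, 48h, 72h and 1w"). The model is: "Study subjects will be considered as random effects, treatment group and visit number as fixed effects". No treatment-by-visit term is listed, and no test or interval is planned at 6 hours.

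**Status of the sample size.** SAP 2.1 and Protocol 3.3.1.2 describe a 10-patient pilot and then a full study "which will be powered according to the outcome of the pilot study". Neither names the contrast to be powered. Protocol 11 describes the work as a pilot with exploratory statistics.

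**Missing data.** SAP 5 removes from any given analysis the subjects who lack data on a variable in that model.

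**The concern.** The quantity used to size the study is not the quantity to be tested. With treatment and visit as main effects only, the model estimates one group difference across all five times. A difference seen mainly at 6 hours is diluted in that average; a lasting difference is estimated more precisely by it. The 90% therefore does not carry over in either direction without further inputs, and neither document says so. The 6-hour comparison itself receives only the descriptive statistics of SAP 6.

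Two things are at stake. First, a null five-visit result could be read as having had a 90% chance of detecting the assumed 9 mm difference, which the documents do not establish. Second, the pilot could re-size the full study on either contrast, and the two may need very different numbers.

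**Working it through.** **1. Reproduce the stated figure.** Inputs from SAP 2.1: 13.9 (SD 16.2), 4.9 (SD 7.3), alpha 0.05, power 90%. Sidedness is not stated; two-sided is inferred because it gives 42 per group, whereas one-sided gives 35.

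- Pooled SD = sqrt((16.2² + 7.3²)/2) = 12.564 mm
- d = (13.9 − 4.9)/12.564 = 0.716
- Two-sided two-sample t-test (noncentral t): n = 41.94, so 42 per group, power 90.0%

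The figure is correct for 6-hour pain. Allowing for the unequal SDs (Welch), 42 per group gives 89.7%.

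**2. What the five-visit effect would need.** Its standardised size is the mean of the five visit differences divided by the SD of a subject's five-visit mean; that SD is the square root of the mean of all 25 entries of the 5 × 5 covariance matrix. From the documents only the 6-hour difference and SD are known. The power is therefore not derivable.

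**3. Illustrative range.** These are assumptions, not figures from the documents: 42 per group, 6-hour difference 9 mm, 6-hour SD 12.56 mm, and the same correlation between any two visits, set at 0.3, 0.5 or 0.7. Each triple of results follows that order.

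| Assumed difference over visits | Assumed SD over visits | Mean difference (mm) | SD of five-visit mean (mm) | Power (%) | n per group for 90% |
|---|---|---|---|---|---|
| 6 h only | constant | 1.80 | 8.33 / 9.73 / 10.95 | 16.5 / 13.3 / 11.5 | 452 / 616 / 780 |
| halves each visit | constant | 3.49 | 8.33 / 9.73 / 10.95 | 47.4 / 36.8 / 30.3 | 121 / 165 / 209 |
| halves each visit | ×1, 0.8, 0.6, 0.4, 0.2 | 3.49 | 5.17 / 5.95 / 6.63 | 86.3 / 75.7 / 66.4 | 48 / 63 / 77 |
| halves each visit | halves, floor ×0.2 | 3.49 | 3.86 / 4.36 / 4.80 | 98.3 / 95.2 / 90.8 | 27 / 34 / 41 |
| constant 9 mm | constant | 9.00 | 8.33 / 9.73 / 10.95 | 99.8 / 98.7 / 96.1 | 20 / 26 / 33 |

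Worked example, second row at correlation 0.5: mean difference = 9 × (1 + 0.5 + 0.25 + 0.125 + 0.0625)/5 = 3.49 mm; SD = 12.564 × sqrt((1 + 4 × 0.5)/5) = 9.73 mm; d = 0.358; power 36.8%.

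The same fading difference gives 30% or 98% depending on the assumed later SDs and correlation. The sign of any gap from 90% is thus unknown.

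**4. Attrition arithmetic.** 50 × 0.8 = 40, below the stated minimum of 42. Keeping 42 needs 42/0.8 = 52.5, so 53 per group. The figure of 50 is close to 42 × 1.2 = 50.4. It covers losses of 1 − 42/50 = 16%, that is 8 of 50.

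| Per group with a 6-hour score | 6-hour power (pooled t) |
|---|---|
| 40 (all 10 losses before 6 h, or lost subjects wholly excluded) | 88.6% |
| 42 (8 lack a 6-hour score) | 90.0% |
| 45 (half the losses after 6 h) | 91.9% |
| 50 (none lost) | 94.4% |

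The Welch figure at 40 per group is 88.2%.

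**The case against.** **The 6-hour basis is disclosed and the size is provisional.** Both true. SAP 2.1 names the 6-hour source, neither document says that the 90% belongs to the mixed model, and the full study is to be re-powered from the pilot. This limits the consequence. It does not remove the point: the 90% is the only power given for a trial whose SAP states a null hypothesis and a primary analysis with a confidence interval, and leaving the re-powering contrast unnamed allows the same mismatch to recur.

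**A null result would be read from its confidence interval.** Largely so, and SAP 6.1 promises one. The statement of power should still match the contrast it appears to support.

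**Sizing on one time point is common.** It is defensible when that time point is tested, or when its link to the primary effect is argued. Neither is done here.

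**The attrition shortfall is a worst case.** This stands. Treatment is a single visit and follow-up runs to 1 week, so a patient lost at 48 hours would still have a 6-hour score. The SAP 5 rule applies analysis by analysis, and a 6-hour comparison needs only that score and the group. The gap is 1.4 points at most, and 50 is stated as a minimum.

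**A stronger reading to avoid.** A reader might infer from the low rows of the first table that the trial is underpowered. The documents do not support that: those rows rest on assumed time courses, SDs and correlations, and other equally undocumented assumptions give power above 90%.

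**Conclusion.** The point holds and is worth fixing. The 90% is correctly computed for a two-group comparison at 6 hours and is not the power of the SAP 6.1 primary contrast. That conclusion needs no outside assumption; it follows from setting SAP 2.1 beside SAP 6.1, and rests only on reading the listed fixed effects as the full set. The size of the discrepancy cannot be fixed from the documents: 12% to 99.8% is an illustration of how far the answer depends on missing inputs, not an estimate.

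The attrition point is secondary and minor. After the stated 20% losses 40 per group remain, not 42. Power at 6 hours is 88.6% only if every loss precedes the 6-hour score or lost subjects are excluded entirely. It is at least 90% if no more than 8 of 50 per group lack that score.

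Two further matters are wording only. SAP 4.1 describes just the pre-treatment score under the primary outcome, although Protocol 6.2 and SAP 6.1 give the five post-operative times. SAP 6.1 ends by promising "The estimated difference in mean change from EndoClean and Control groups" after defining a mean difference; with preoperative scores limited to 0–4 mm, this has little numerical effect.

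**What to change.** Before outcome data are seen:

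1. In SAP 2.1 and Protocol 3.3.1.1, state that the 90% applies to the 6-hour comparison and not to the SAP 6.1 contrast. Alternatively, recompute it for the five-visit average with the assumed time course, SDs and correlation written down.
2. In the same place, state that 50 per group less 20% leaves 40, with 6-hour power as low as 88.6% if all losses precede the 6-hour score.
3. Where SAP 2.1 and Protocol 3.3.1.2 describe re-powering from the pilot, state that the full study will be powered on the SAP 6.1 primary contrast.
4. In SAP 6.1, keep the five-visit average as primary and add the 6-hour difference with its 95% CI (Welch comparison) as a named secondary contrast.

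Wording: in SAP 4.1 name the post-operative VAS scores at the five times as the primary outcome, and in SAP 6.1 use mean difference over the five visits throughout.

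The cost is a few sentences and one secondary contrast from data already collected. The power statement becomes less favourable or rests on declared assumptions. No extra patients are needed; if the sponsor prefers to keep 42 per group after 20% losses, 53 per group means 6 more in total.

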3.3.1.2. Pilot Study

10 patients will be involved in a pilot study. There will be 5 patients in each group: manual final irrigation and EndoClean device. Pilot study will be conducted for two reasons. The first reason is to ensure the safety of the device for clinical use. Thesecond reason is to conduct an accurate power analysis and therefore, a sample group for the full clinical study. A full clinical investigation will be performed once the pilot study is done, and which will be powered according to the outcome of the pilot study.

3.3.1.3. Inclusion Criteria:

1. Physical status classification system described was used for patients' recruitment. Healthy patients, who were classified by the American Society of Anaesthesiologists (ASA) as ASA I and II
2. Patients with the age of 18 and over
3. Patients who were diagnosed as in need of non-surgical orthograde root canal treatment of an asymptomatic tooth
4. Tooth without signs of previously initiated Root Canal Therapy

3.3.1.4. Exclusion Criteria:

1. Pregnant and lactating females
2. Patients with chronic periodontal diseases
3. Patients with sensitivity or adverse reactions to any medication or materials that were used throughout the treatment procedure
4. Patients with acute periapical periodontitis
5. Patients with acute periodontal abscess
6. Patients who could not abide by the follow-up time
7. Patients who used analgesics 1-week prior or antibiotics 1-month prior to treatment
8. Uncooperative patients
9. Teeth that cannot be made functional nor restored or difficult to access teeth with no importance (wisdom teeth)
10. Teeth with poor prognosis, for example, due to deep root caries or big root resorption
11. Teeth with ≥ 4 mm periodontal pocket depth
12. Teeth with an inaccessible root end
13. Teeth with apical resorption or a radiologically not clearly defined apex
14. Fractured teeth
15. Teeth with immature or open apices
16. Teeth with root apices extending into the maxillary sinus

17. Teeth with external resorption communicating with the pulp

3.3.1.5. Withdrawal Criteria:

Subjects may be withdrawn from the study at the discretion of the Investigator or Sponsor due to a safety concern or if judged non-compliant with trial procedures.

A subject must be withdrawn from treatment if one of the following applies:

- Subject chooses to withdraw from the study at any time;
- Intolerable adverse effects;

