3.5. Randomization and Blinding

The patients will be randomly assigned to one of the two groups based on the irrigation protocol (Group 1-named "CONI" (conventional irrigation), and Group 2- named "INCA" (inertial cavitation)). To rule out the potential influence of the tooth type (molar, nonmolar) on postoperative pain, stratified randomization will be performed (**Nagendrababu & Gutmann 2017**). Blocks with different sizes of 2, 4 and 6 and an allocation ratio of 1:1 will be prepared (<https://www.randomizer.org>).

All allocations containing the unique randomization number and group name (CONI or INCA) will be concealed in opaque sealed envelopes which will be marked with the abbreviations "M" (molar) and "NM" (non-molar).

Due to the nature of the study, both patient and the operator could not be blinded to the treatment protocol. However, the data collector will be blinded to the objectives and the design of the study.

4. Patient information and informed consent to participate:

All patients participating in the study have to be informed in oral form by the Investigator. Additionally, patients will receive an information form, on which they shall give their written consent to participate in the investigation. This form will be countersigned by the Investigator and the Patient.

5. Confidentiality:

Data will be collected with a browser-based electronic data capture system. No personal data such as name, address, date of birth will be collected with this system. The data will be accessible to the sponsor within this system. The identification codes, used by the "Investigator" to put the results of the study in a certain relation, have to be kept confidential by the Investigator after completion of the study.

6. Clinical Procedures

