Statistical analysis will be defined on later stage. It is a pilot study with exploratory statistics.

12. Financing and Insurance

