4.1 Primary Outcome: All participants will be asked to grade their pain intensity level on a horizontal Visual Analogue Scale (VAS) before the treatment procedure. This scale is a horizontal 100 mm bar, marked in every 10mm with two ends. One end (0) indicated “no pain” and the other end (10) indicated “worst pain possible”. Categorization of pain scores is as follows: 0-4 mm = No Pain, 5-44 mm = Mild Pain, 45-74 mm = Moderate Pain, 75-100 mm = severe pain. After grading the pain level, the distance between the marked point and the “no pain” endpoint will be measured with a ruler to calculate the pain intensity level. Clinical and radiological findings consistent with the asymptomatic tooth with nonvital pulp tissue with the preoperative pain intensity scores in the category of “no pain” will be included in the study.

4.2 Secondary Outcome: If excessive pain will be experienced by three concomitant patients the study will be terminated.

5. Populations to be Analysed

Data of all randomised study subjects will be analysed. This will be seen as the primary population for the analysis. For any specific analysis, study subjects with missing data on any of the variables in the model will be excluded from the analysis.

6. Analyses

All outcomes will be presented using descriptive statistics; normally distributed data by the mean and standard deviation (SD) and skewed distributions by the median and interquartile range (IQR). Binary and categorical variables will be presented using counts and percentages. Python programming language and its dependent statical libraries will be used for all statistical analysis.

The subsections below will describe analyses in addition to the descriptive statistics.

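### The primary model omits the molar/non-molar randomisation stratum and admits covariates by an undefined, response-driven rule, so it is not unique and may be less precise than it could be

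*SAP*

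**What the plan says.** Protocol section 3.5 gives the reason for stratifying: "To rule out the potential influence of the tooth type (molar, nonmolar) on postoperative pain, stratified randomization will be performed". Allocations are 1:1 in blocks of 2, 4 and 6, and they are "concealed in opaque sealed envelopes which will be marked with the abbreviations" M and NM. The stratum is therefore on record for every randomised patient.

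SAP section 6.1 names these model terms: "Study subjects will be considered as random effects, treatment group and visit number as fixed effects". On anything further it says: "Other variables like Age and Toot-ID can be included as a covariate according to their relations with response variable". The SAP mentions neither the stratification nor molars.

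Protocol section 11 does not fill the gap: "Statistical analysis will be defined on later stage". SAP 6.1 is thus the only specification of the primary model. SAP section 5 adds that "study subjects with missing data on any of the variables in the model will be excluded from the analysis".

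**The concern.** There are two linked problems.

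1. **The model is not unique.** The covariate list is open, inclusion is optional, and the plan gives no test, threshold, coding or time of decision. The tooth variable could be the molar/non-molar indicator, a tooth number, or one category per tooth. Two statisticians could follow the SAP faithfully and report different primary estimates. Operator and patient are unblinded, and the SAP does not say that covariates are chosen before allocation is known to the analyst.

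2. **The analysis does not follow the randomisation.** Stratifying balances tooth type between the arms. If tooth type predicts pain and is left out, the variance it explains stays in the residual. The standard error is then too large, the 95% interval is conservative, and some power is lost.

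The complete-case rule in SAP section 5 adds a smaller point: an open covariate list also leaves the analysed set partly open.

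**Working it through.** **The plan's own figure.** The inputs are in SAP section 2.1: means 13.9 and 4.9, SDs 16.2 and 7.3, alpha 0.05, power 90%. Pooled SD = √((16.2² + 7.3²)/2) = 12.56, and d = 9.0/12.56 = 0.716. A two-sided two-sample t-test (noncentral t) needs 42 per group, with power 90.0%. The stated 42 per group reproduces.

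**Omitting the stratum.** With complete, balanced visits, the treatment effect in a random-intercept model equals the difference in patient means. Let R² be the share of between-patient variance explained by tooth type. The documents give no value, so 0% to 15% is assumed.

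- Standard-error factor with the stratum omitted: 1/√(1 − R²).
- Noncentrality: 0.716/√(1 − R²) × √(42/2), taking d = 0.716 against the overall SD.
- With the stratum, the critical value is t on 81 df. Without it, the true sampling error is the same, but the critical value (82 df) is in effect multiplied by 1/√(1 − R²).

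Example at R² = 10%: the factor is 1/√0.90 = 1.054. Noncentrality is 0.7547 × 4.583 = 3.459. The critical value without the stratum is 1.989 × 1.054 = 2.097, so type I error is 3.9% and power 91.2%.

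| R² | SE excess | Type I error, stratum omitted | Power without | Power with |
|---|---|---|---|---|
| 0% | 0% | 5.0% | 90.0% | 90.0% |
| 5% | 2.6% | 4.5% | 90.6% | 91.4% |
| 10% | 5.4% | 3.9% | 91.2% | 92.8% |
| 15% | 8.5% | 3.4% | 91.7% | 94.0% |

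With equal strata, R² = 0.25D²/(1 + 0.25D²), where D is the molar effect in within-stratum SDs. R² of 5%, 10% and 15% then means D of 0.46, 0.67 and 0.84. Fitting the SAP's structure directly (random intercept, five visits, 84 patients, 40 fits per R²) gave SE excesses of −0.1%, 2.4%, 4.7% and 7.8%, in line with the formula.

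**Applying the covariate rule mechanically.** The SAP gives no threshold, so entry at p<0.05 is assumed (4,000 simulated trials per scenario). Results at R² = 5%, 10%, 15%:

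- *Coded molar/non-molar:* selected in 55%, 86%, 97% of trials. Mean SE is within 0.3% of the model that includes the stratum.
- *Entered as a two-digit tooth number:* it carries 2.4% of the molar contrast and is selected in 6–9% of trials. SE stays 2.5%, 5.3%, 8.5% too large.
- *Entered as 28 categories* (permanent teeth without wisdom teeth, an assumption): selected in 13%, 25%, 42% of trials. Mean SE is 3.2%, 6.5%, 9.9% larger. Power is 89–90%, against 91.4–94.0% in the table with the stratum.

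Type I error was 3.6–5.2% throughout, with Monte Carlo error of about 0.35 points.

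**How often the choice changes the answer.** Four models (with or without stratum, with or without age) disagreed on p<0.05 in 2.5–3.5% of trials at d = 0.716 and in 5–9% at d = 0.45. A separate simulation used three candidate covariates, hence 2³ = 8 models, at 84 patients. They disagreed in 2.4–4.2% of runs with no treatment effect and in 11.0–15.6% of runs with a true effect of 0.5 SD. Selecting by relation with the response kept type I error near 5%. Choosing the most favourable of the eight models raised it to 6.0–6.4%.

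**The case against.** The strongest reply is that a tooth variable is already contemplated. If it means molar/non-molar, the rule recovers the stratum with almost no loss. That is correct for that coding, but the SAP does not adopt it, and the variable remains optional.

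The precision loss is also small. Power without the stratum is at least the planned 90% in every case, the interval errs on the safe side, and every non-zero figure rests on an assumed tooth-type effect. This stands, and it makes non-uniqueness the stronger half of the point. The tooth-number and 28-category codings are illustrations that no document proposes. They show only that the result depends on an unstated choice.

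The analysed-set point is weak for the named covariates. Age is recorded at diagnosis, and tooth type must be known to pick the envelope. Only unnamed further variables could remove patients.

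Finally, protocol section 11 calls this an exploratory pilot, and the first stage has 10 patients. The figures here do not describe that pilot. They address the 84-patient calculation that the SAP carries. Since the SAP states a null hypothesis and a primary analysis, one defined model is still needed.

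**Conclusion.** The concern holds. The SAP does not pre-specify the factor that the protocol chose to stratify on, and its covariate rule permits several primary models. That conclusion comes from the text and needs no assumed effect.

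The numerical cost is modest and conditional. Omission makes the standard error 0% to 8.5% too large and costs up to about 2 points of power, for R² between 0% and 15%, 42 per group, d = 0.716 (the 6-hour planning value, used as an illustration), and normal data with equal variances. Omission does not bias the treatment estimate, and the rule does not inflate type I error unless models are chosen by their treatment result. The change should be made, but the trial does not stand or fall on it.

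**What to change.** Rewrite SAP section 6.1 so that the primary model has treatment, visit and molar/non-molar (as randomised) as fixed effects, with the subject random effect. State now whether age is in, and in what form, or leave it out. Delete the clause that lets covariates enter by their relation with the response. Define the tooth variable, and label any model with tooth identity or further covariates as a sensitivity analysis.

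The cost is SAP wording and one degree of freedom. No new data are needed, because the stratum is already marked on the envelopes, and adding it excludes no patient under SAP section 5.
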